## 4.1.3 Pooling of centres

No pooling of centres will be performed.

## 4.1.4 End of Study

A patient is considered to have completed the study if he/she has completed all visits of the study (until visit 6).

The end of the study is defined as the date of the last visit of the last patient in the study.

## 4.2 Patient disposition

The disposition of patients will be summarized using the following tabulations:

- the number of all screened subjects (included in Visit 0 ICF signed)
- the number of screening failures with reasons of exclusion
- the number of randomised subjects (at Visit 1)
- the number of subjects who took at least one dose of IMP
- the number of subjects who prematurely discontinued the study i.e. withdrawals with reasons (Adverse Events, non-compliance to IMP, Protocol selection criteria violation, Consent withdrawn, others)
- the number of patients who completed V5 (primary endpoint assessment at the end of maintenance dose)
- the number of subjects having completed the entire study until Visit 6

Then this will define the number of subjects in the ITT, Safety, mITT and PP population.

Frequencies or different reasons for exclusions from analysis sets (as defined in section 3) will be tabulated and listed.

A CONSORT flow diagram on patient disposition, will be created in the CSR.

Statistical Analysis Plan	Version 1.0		Page 15 of 37
Sponsor	SOM Biotech	Protocol No	SOMCT03

Also, the disposition by country and centre will be presented.

A by-patient listing of the randomisation scheme and codes will be provided.

#### 4.3 Demographic and other background data

## 4.3.1 Basic description

**Demographic and baseline characteristics** will be summarized in frequency or sampling statistics tables for Safety population (SAF) and mITT, if not identical.

Screen failure demographic data will be also listed.

Demographic variables:

- Age
- Sex
- BMI
- Ethnic origin
- Country and centre
- Females only: childbearing potential (Yes/No)

## Disease specific patient characteristics measured at screening/baseline:

- Number of Cytosine-Adenine-Guanine (CAG) repeats
- Total Functional Capacity (TFC) score at baseline
- Level of chorea at baseline (TMC score)
- Total Motor score (TMS) at baseline
- Age at diagnosis: Year of HD diagnosis Year of Birth, where year of birth will be calculated as: Year of inform consent Age
- Age at first symptoms: Year of first symptoms Year of Birth, where year of birth will be calculated as: Year of inform consent Age
- Documented evidence on any other HD-related symptom(s) available such
  - o Presence of depression
  - o Presence of Behaviour disorders or aggressiveness
  - Presence of Cognitive disturbance
- Neuroleptic treatment in co-medications to treat behaviour disorder (accepted by Steering Committee)
- Antidepressant treatment in co-medications

Antidepressant and neuroleptic treatments will be identified by the Sponsor and Medical Monitor.

Statistical Analysis Plan	Version 1.0		Page 16 of 37
Sponsor	SOM Biotech	Protocol No	SOMCT03

## 4.4 IMP exposure and compliance

## **Exposure:**

- Total number of patients with at least one dose of study treatment: overall and per treatment periods (W1 (200mg once daily (OD) or Placebo), W2 (200mg BID or Placebo), W3 (200 or 300mg BID or Placebo), W4-W10 (200 or 300mg BID or Placebo), W11 (200mg OD or Placebo), W12 (Placebo))
- Total number of days with at least one dose of study treatment: overall and per treatment periods (W1 (200mg OD or Placebo), W2(200mg BID or Placebo), W3, W4-W10 (200 or 300mg BID or Placebo), W11(200mg OD or Placebo), W12 (Placebo)).

The earliest date of study withdrawal/completion or product withdrawn (AE) will be selected and the day before this date will be defined as the last treatment intake. The first date of administration is collected by visit in the eCRF. Within visits, the intake of study treatment will be defined according to the study protocol and is theoretical.

## **Compliance:**

Compliance will be evaluated by calculating at each visit the number of capsules used (capsules dispensed minus capsules returned) divided by the expected number of capsules to be used x 100. A patient will be deemed compliant if the patient has taken  $\geq$ 80% but  $\leq$ 120% of the expected tablets of study drug.

Total dose taken per patient and per bottle can be calculated as:

Total dose (mg) for each bottle = (total number of capsules in the bottle – number of capsules returned) x dose for the given bottle

Compliance (%) will be assessed during the whole study and by study period (up-titration period W1-W3 (from V1 to V2), maintenance period W4-W10 (from V2 to V5), and down-titration period W11-W12 (from V5 to V6).

A summary of the total dose by study period and IMP compliance (%) by study period will be presented per treatment group for the SAF.

A by patient listing of IMP compliance by period will be provided.

## 4.5 Medical history, physical examination

All medical history and physical examination data will be listed.

Analysis of physical examination is described in Section 4.10.5.

#### 4.6 Prior and concomitant medication

Prior and concomitant medications will be coded using the WHO Drug Global thesaurus version Q1 2022. Coding will be performed by Ergomed and agreed upon with the sponsor before data base lock (cf. DMP).

Prior medications are defined as medications which were taken before the study and stopped before the start of study treatment. For some drugs they should be stopped 1 or 3 months before the randomization as stated in protocol §5.3.1.

Statistical Analysis Plan	Version 1.0		Page 17 of 37
Sponsor	SOM Biotech	Protocol No	SOMCT03

Concomitant medications are defined as medications which were taken during the study with the investigational treatment (regardless of the start time).

Prior medications and Concomitant medications will be listed separately. Summaries will show the frequencies of patients by WHO Drug Global INN.

All details of concomitant medications will also be listed including the route, dose, frequency, start and stop date and indication.

Analysis of concomitant medications is described in Section 4.10.6.

## 4.7 Efficacy

The primary efficacy analysis will be conducted on the mITT population including all patients who were randomized to treatment, received at least one dose of study drug and had at least one post-baseline assessment of the TMC score. Patients will be included in the treatment group to which they were randomized, regardless of the treatment that was received.

Additional analyses for the primary endpoint will also be performed for the ITT population and PP population. The latter analyses serve as sensitivity analysis to explore the robustness (cf. Section 2.1).

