- Primary endpoint will be analyzed for the ITT Population using a multiple imputation.
- Primary efficacy analysis will be repeated for the PP Population.

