## 2.2 Deviations from the trial protocol with regard to statistical analyses

The following deviations from the protocol were identified as being important for the statistical analysis:

For the key secondary efficacy endpoint (Change from baseline in the Clinical Global Impression (CGI-C)) multiplicity adjustment will be applied.

Original text in protocol: The type I error will be set at 0.05 (two-sided) and the coverage level of confidence intervals to 95% for all secondary efficacy analyses. No multiplicity adjustment will be applied for the statistical inferences of the secondary efficacy endpoints.

Statistical Analysis Plan	Version 1.0		Page 9 of 37
Sponsor	SOM Biotech	Protocol No	SOMCT03

The revised definition in SAP only for key secondary endpoint: To preserve the family-wise error rate at the 0.05 level when comparing the two doses of SOM3355 versus placebo and comparing a primary endpoint and key secondary endpoint, statistical testing will be carried out using the Holm procedure for CGI-C if the primary endpoint is significant for both doses. The smallest p-value of the two comparisons will be first compared at the two-sided 0.025 level and if statistically significant, the other p-value will be compared at the two-sided 0.05 level.

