## 3.2 Intention-to-Treat (ITT) population

The ITT Population will include all randomized patients whether they received the study treatment or not. Patients will be analysed in the treatment group to which they were randomized, regardless of the treatment that was actually received or if they withdrew prior to first dosing.

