## Sensitivity #1

A sensitivity analysis will be performed to assess the robustness of the primary analysis based on MMRM. Intermittent missing values will first be imputed using the Markov Chain Monte Carlo (MCMC) method which assumes a joint multivariate normal model for variables in the imputation model. Then a control-based pattern imputation is applied to the monotone missing data under the assumption of data missing not at random (MNAR). PROC MI using the MCMC statement will be used to implement the first step. Then PROC MI using the MONOTONE and MNAR statements will be used to create the complete data sets. MNAR will be imputed using Copy Reference method and number of imputations will be 30. The same MMRM analysis as defined for the primary analysis will be performed on the complete data sets, and the results will be combined using PROC MIANALYZE. This analysis will be performed on the mITT population.

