## Sensitivity #3

Primary efficacy analysis will be repeated for the PP Population.

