## Sensitivity #4

The primary efficacy analysis will be repeated using data without imputation for the visits of discontinued patients for the mITT population.

Subgroup analysis as defined in section 3.6 will be performed for the primary endpoint across all predefined groups, with a particular focus on comparing patients taking neuroleptics as concomitant medication during the study versus patients not taking neuroleptics during the study. For this subgroup, descriptive statistics for the TMC score and changes

Statistical Analysis Plan	Version 1.0		Page 20 of 37
Sponsor	SOM Biotech	Protocol No	SOMCT03

from baseline by treatment group and by visit (including V6) will be presented, as well as time profiles of the mean TMC scores with standard error of the mean (SEM) will be provided.

For the subgroup analysis assessing patients with correct versus incorrect down titration phase between V5 and V6, only descriptive statistics for TMC score on visits will be repeated on the mITT to show the evolution of the TMC score between V5 and V6 after IMP interruption.

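### SAP 4.7.1 specifies no ITT analysis of the primary endpoint, although Protocol 9.4.1 requires one and SAP 4.7 still promises one; the change is not declared

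*SAP*

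**What the plan says.** Protocol 9.4.1 names three sensitivity analyses of the primary endpoint: an observed-case ANCOVA, a PP repeat, and this one: "Primary endpoint will be analyzed for the ITT Population using a multiple imputation". It does not say which kind of multiple imputation.

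SAP 4.7 makes mITT the primary population and adds: "Additional analyses for the primary endpoint will also be performed for the ITT population and PP population". It points to Section 2.1 for these analyses, but that section describes data transfer and SAP finalisation and contains no ITT method.

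SAP 4.7.1 then specifies four sensitivity analyses:

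- **#1**: MCMC for intermittent gaps, then a control-based step: "MNAR will be imputed using Copy Reference method and number of imputations will be 30". Its population: "This analysis will be performed on the mITT population".
- **#2**: observed-case ANCOVA, on mITT.
- **#3**: "Primary efficacy analysis will be repeated for the PP Population".
- **#4**: the primary analysis "repeated using data without imputation for the visits of discontinued patients for the mITT population".

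SAP 3.2 defines ITT broadly: "The ITT Population will include all randomized patients whether they received the study treatment or not". SAP 3.4 requires a dose and at least one post-baseline TMC for mITT, and SAP 3.5 makes PP a subset of mITT.

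SAP 2.2 opens with "The following deviations from the protocol were identified as being important for the statistical analysis" and lists one item, the multiplicity adjustment for CGI-C.

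**The concern.** A patient belongs to mITT only if a TMC score was obtained after randomisation, so membership can depend on treatment. The first scheduled post-baseline TMC is Visit 2 (Day 21), at the end of up-titration. Protocol 4.3 gives reduction of the risk of hypotension or bradycardia at the start of treatment as a reason for titrating, and Protocol 5.7 names both among the events that may end participation. Early loss could therefore differ between arms. The protocol planned an analysis able to show how much the mITT restriction matters, and the SAP does not specify it.

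The general sentence in 4.7 does not fill the gap. A patient with a baseline TMC only contributes no outcome row to the MMRM, so running the primary model on the ITT population without imputation adds nothing from that patient. These patients enter the estimate only through imputation, and the SAP's imputation starts from a population that has already lost them. Someone programming from 4.7.1 would produce no ITT result, or would have to choose a method that the plan does not state.

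**Working it through.** **1. Populations side by side**

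| Analysis of the primary endpoint | Protocol 9.4.1 | SAP 4.7.1 |
|---|---|---|
| Primary MMRM | mITT | mITT |
| Multiple imputation | ITT | mITT (#1, copy reference) |
| Observed-case ANCOVA | not named in that line | mITT (#2) |
| Per-protocol repeat | PP | PP (#3) |
| No imputation for discontinued patients' visits | not listed | mITT (#4) |

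Sensitivity analyses specified on ITT: 1 of 3 in the protocol, 0 of 4 in the SAP. Subgroup analyses (SAP 3.6) use mITT, with the neuroleptic subgroup also on PP. Secondary endpoints (SAP 4.7.2) use mITT, some also PP. Because PP lies inside mITT, every specified efficacy analysis omits the same patients.

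**2. Who is omitted**

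ITT minus mITT consists of (a) randomised patients never dosed and (b) dosed patients with no post-baseline TMC. Group (a) should be rare, because Protocol 8.1.2 has the first dose given during Visit 1. Group (b) is reduced by Protocol 5.7, which asks for end-of-treatment assessments on discontinuation whenever possible, and by SAP 4.1.2, which assigns an end-of-study value (or a last unscheduled value) to the first missing visit. What remains is mainly patients lost before Day 21 without an exit rating.

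**3. The plan's own figure**

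Inputs (Protocol 9.2 and 9.3, SAP 1.4): difference -2.5, SD 3.5, two-sided 0.025, t-test. Noncentral t power is 0.794 at 38 per arm and 0.805 at 39, so the stated 39 is reproduced for one dose-placebo comparison. 39 × 1.10 = 42.9, which rounds to the stated 43. The planned loss is 43 - 39 = 4 per arm.

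**4. Size of the effect (assumed range)**

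The documents give no count of patients without a post-baseline TMC. Let k be that number in an active arm of 43, and suppose copy reference places them at the placebo mean, so that their expected treatment difference is zero. Then

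difference = -2.5 × (43 - k) / 43, a shift of 2.5 / 43 = 0.058 points per patient.

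| k | Difference | Power of the pairwise t-test, 43 per arm, two-sided 0.025 |
|---|---|---|
| 0 | -2.50 | 84.6% |
| 1 | -2.44 | 82.8% |
| 2 | -2.38 | 80.8% |
| 3 | -2.33 | 78.6% |
| 4 | -2.27 | 76.3% |

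Power is computed at 43 per arm because an imputed all-randomised analysis includes everyone. It is shown only for scale, since a sensitivity analysis does not decide the trial. The value k = 4 would need essentially all the planned dropout in that arm to occur before Visit 2 with no exit rating.

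**The case against.** The strongest reply is that nothing has been withdrawn. The ITT promise survives in SAP 4.7 and the protocol's line still stands, so a reader who infers that the ITT analysis was abandoned goes further than the text. The same holds for inferring that multiple imputation was dropped: it was kept, given a stricter assumption, and moved to mITT. Both limits are accepted. What stands is that the promised analysis has no model, imputation rule or handling of baseline-only patients anywhere in the SAP, and that SAP 2.2 is silent.

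Second, Sensitivity #1 is stated as a check on the primary MMRM, which uses mITT, and the estimand table applies the discontinuation strategy to randomised and treated patients. Holding the population fixed while changing the missing-data assumption is legitimate, and #1 does stress dropout after Visit 2. This is a reason to keep the mITT run. It does not replace the protocol's ITT analysis.

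Third, a reader might infer that early safety withdrawals will bias the active arms. The documents do not show this. Protocol 2.2.1 says that the most frequent adverse events in the earlier HD trial were mild or moderate and did not lead to treatment withdrawal. The 600 mg/day dose was not studied in that trial, so the mechanism remains possible, but no document gives an early-loss rate.

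**Conclusion.** The point holds as an undeclared mismatch between protocol and SAP and a contradiction between SAP 4.7 and 4.7.1. As specified, no efficacy analysis tests the exclusion of randomised patients without a post-baseline TMC. It would be too strong to say that these patients appear in no analysis at all, because those who were dosed remain in the safety population.

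The numerical effect is probably modest: about 0.06 points per affected active-arm patient, so at most 0.12 points for 0 to 2 per arm and 0.23 points for 4. These figures rest on an assumed count and on zero treatment difference in the patients concerned. The primary analysis is not shown to be biased. The correction should be made because the protocol committed to the analysis and the method should be fixed before unblinding.

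**What to change.** 1. In SAP 4.7.1, run Sensitivity #1 also on the ITT population: all randomised patients with a baseline TMC, including baseline-only and undosed patients, with every missing post-baseline visit imputed by copy reference, 30 imputations and the same MMRM. A TMC score is an entry criterion, so a missing baseline should be very rare. Keep the mITT run beside it.
2. In SAP 2.2, record that the multiple imputation the protocol left unspecified is now done by copy reference, and that it is run on both populations.
3. In SAP 4.7, replace the reference to Section 2.1 with one to the sensitivity analyses in 4.7.1.

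If the sponsor prefers not to run the ITT version, the minimum is to delete the promise in 4.7 and justify the omission in 2.2, but this leaves the exclusion untested.

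The cost is a few sentences, one extra run and a slightly more conservative sensitivity estimate. The primary analysis and the sample size are unchanged.

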## 4.7.1 Primary endpoint

The primary endpoint is the change in Total Maximal Chorea (TMC) score from baseline (defined for each patient as the average of values at the screening visit (Visit 0) and the inclusion visit (Visit 1)) to the end of maintenance therapy (defined for each patient as the average of values at the end of Week 9 (Visit 4) and the end of Week 10 (Visit 5)).

As a result, the different factors included in the MMRM model (below) will be defined as following:

- Baseline TMC: calculated as (TMC V0 + TMC V1)/2,
- TMC at each following Visits: V2 (week 3), V3 (week 6), V4 (week 9), V5 (week 10)),
- Change from baseline TMC: [(TMC V4 + TMC V5)/2 Baseline TMC]

If the value at V5 is missing and V4 is not missing, then the value at V4 will be used for the calculation. If the value at V4 is missing and V5 is not missing, then the value at V5 will be used for the calculation. If both V4 and V5 values are missing, change from baseline TMC will be treated as missing.

The estimand of the primary efficacy analysis is defined according to ICH-E9-R1. The estimand reflects a mixed strategy for the inter-current events as presented in the table below.

Estimand attribute	Primary definition	Rationale (as needed)
Population	Patients with Huntington's disease with choreic movements	

Statistical Analysis Plan	Version 1.0		Page 18 of 37
Sponsor	SOM Biotech	Protocol No	SOMCT03

Estimand attribute	Primary definition		Rationale (as needed)
Endpoint	Change from baseline (Visit 0 and Visit 1) to end of maintenance dose (Visit 4 and Visit 5) in TMC score		
	Event	Strategy	Rationale (as needed)
	Receipt of assigned study treatment	Treatment policy	This strategy applied to align the estimand with the application of the ITT principle.
Inter-current events	Prohibited concomitant neuroleptic treatment during the treatment period	While on treat- men	This strategy applied up to the time of the prohibited concomitant treatment.
	Discontinuation from study	Hypothetical policy	This strategy applied for randomized and treated patients using a MMRM approach under MAR assumptions.
Summary measure	Difference in the change of TMC score from baseline to end of maintenance visit adjusted LS means between active arms and placebo		

The primary analysis of the primary efficacy endpoint will be based on a mixed-effect linear model for repeated measures (MMRM) to compare each active treatment group to placebo. The model will include the following factors: treatment group, visit, and treatment-by-visit interaction as fixed effects, and baseline TMC score as covariate. An unstructured (UN) variance-covariance matrix will be used to model the within-patient errors. If no reliable results under the UN assumption can be obtained, the Toeplitz (TP) covariance structure, followed by the autoregressive (AR1) and Compound Symmetry (CS) covariance structure will be used. The Kenward-Roger method will be used to estimate the denominator degree of freedom.

The SAS code for the primary analysis is as follows:

PROC MIXED data=dataset method=REML;

CLASS subject treatment visit;

MODEL changeTMC = treatment visit treatment\*visit baselineTMC / ddfm=KR;

REPEATED visit / subject = subject type = UN;

LSMESTIMATE treatment\*visit "TMC change 200 mg vs Placebo" 0 0 -1 0 0 1 0 0 0 / cl elsm;

LSMESTIMATE treatment\*visit "TMC change 300 mg vs Placebo" 0 0 -1 0 0 0 0 0 1/cl elsm:

RUN;

Statistical Analysis Plan	Version 1.0		Page 19 of 37
Sponsor	SOM Biotech	Protocol No	SOMCT03

The least squares mean (LSM) estimate for each treatment group and difference in LSM estimates at end of maintenance dose between active treatments and placebo group with their confidence intervals will be provided. For the lowest p-value 97.5% CI will be provided and for the highest p-value 95% CI will be provided.

To preserve the family-wise error rate at the 0.05 level when comparing the two doses of SOM3355 versus placebo, statistical testing will be carried out using the Holm procedure. The smallest p-value of the two comparisons will be first compared at the two-sided 0.025 level and if statistically significant, the other p-value will be compared at the two-sided 0.05 level.

Descriptive statistics will be presented for the TMC score and changes from baseline by treatment group and by visit (including V6), on imputed data (as described in 4.1.). In addition, time profiles of the mean TMC scores with standard error of the mean (SEM) will be presented.

Sensitivity analyses on the primary efficacy endpoint will be conducted as follows:

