## 4.7.2.3 The percentage of change in TMC score

The percentage of change in TMC score is defined as:

100 \* (TMC score at Visit x – TMC score at Baseline) / TMC score at Baseline. CONFIDENTIAL

Statistical Analysis Plan	Version 1.0		Page 22 of 37
Sponsor	SOM Biotech	Protocol No	SOMCT03

"Baseline" is the average score between V0 and V1, "Visits x" are V2, V3 and the average score between V4 and V5 or V4, V5 in case of missing visit.

For the analysis of the percentage of change in TMC score, descriptive statistics and the same MMRM model, as described for the primary endpoint will be used.

This analysis will be repeated on the PP population.

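### Does SAP 4.7.1 put the primary MMRM contrasts at risk by listing four visits while the printed code has nine coefficients?

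*SAP*

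**What the plan says.** SAP 4.7.1 defines the primary endpoint as the change in TMC from the mean of V0 and V1 to the mean of V4 and V5. It then sets out the MMRM inputs:

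- baseline TMC;
- the post-baseline scores, "TMC at each following Visits: V2 (week 3), V3 (week 6), V4 (week 9), V5 (week 10";
- the response, "Change from baseline TMC: [(TMC V4 + TMC V5)/2" minus baseline.

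Two rules cover missing end-of-maintenance scores. "If the value at V5 is missing and V4 is not missing, then the value at V4 will be used for the calculation", and the reverse applies when only V4 is missing. "If both V4 and V5 values are missing, change from baseline TMC will be treated as missing".

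The code has "CLASS subject treatment visit" with no ordering option, and two labelled contrasts:

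- 200 mg versus placebo: "0 0 -1 0 0 1 0 0 0 / cl elsm";
- 300 mg versus placebo: "0 0 -1 0 0 0 0 0 1/cl elsm".

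Section 4.7.2.3 applies the primary endpoint's MMRM to percentage change and says that its visits "are V2, V3 and the average score between V4 and V5 or V4, V5 in case of missing visit". Under Listings, SAP section 4 sorts the arms as placebo, 200 mg BID, 300 mg BID.

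**The concern.** Read alone, the list in 4.7.1 suggests a visit factor with four levels. The contrasts do not fit four levels, and they also depend on an arm order that the section does not give. The response is written out only for the V4/V5 average, so the change at V2 and V3 is not defined there. Nor does the both-missing rule say that V2 and V3 stay in the model for such a patient.

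Two other places add to the doubt. Section 3.6 describes the primary endpoint for subgroups as being at V5. Section 4.12 takes its method and code from Section 4.6.1 and an Appendix 2, but 4.6 covers prior and concomitant medication and only Appendix 1 exists.

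At stake is the confirmatory test of both doses. The same model also serves Sensitivity #1, #3 and #4, the percentage-change analysis and the futility analysis. If visit were coded with four levels, or if placebo did not come first, the printed rows would compare the wrong weeks or the wrong arms under correct-looking labels.

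**Working it through.** **Inputs.** Three arms. Nine coefficients per row, non-zero at positions 3 and 6 (row 1) and 3 and 9 (row 2). Treatment precedes visit in CLASS, so visit varies fastest. All are from the code in SAP 4.7.1.

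**Number of levels.** With L visit levels there are 3 × L cells. Nine coefficients give L = 9 / 3 = 3. The four listed visits would give 3 × 4 = 12.

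**Cells selected.** Position = (arm rank − 1) × L + visit rank. For L = 4 the last three coefficients are taken as zero.

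| Position | L = 3 | L = 4 |
|---|---|---|
| 3 | arm 1, third level | arm 1, third level (V4) |
| 6 | arm 2, third level | arm 2, second level (V3) |
| 9 | arm 3, third level | arm 3, first level (V2) |

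With L = 3, levels V2, V3 and the V4/V5 mean, and arms placebo, 200 mg, 300 mg, row 1 is 200 mg minus placebo at end of maintenance and row 2 is 300 mg minus placebo at end of maintenance. Both match their labels. Taking all six arm orders with three and with four levels gives 12 layouts, and this is the only one that matches both labels.

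**Does the SAP lead to that layout?**

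- The V2–V5 item lists raw scores. V4 and V5 have to appear there because the next item averages them.
- With four levels, the average and the rule for a single missing visit would have no role in the model.
- Section 4.7.2.3 names V2, V3 and the V4/V5 average, with a formula for any visit, under the primary endpoint's model.
- One change value per patient would leave nothing for the REPEATED statement to repeat. Section 4.7.1 also asks for descriptive changes from baseline by visit. So change at V2 and V3 is intended.
- The mITT set needs only one post-baseline TMC score, and the estimand handles study discontinuation by MMRM under MAR. Dropping V2 and V3 when V4 and V5 are both missing would contradict both.
- The arm order follows from the contrast labels and agrees with the listing order.

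**What a miscoding would do.** Take the planned effect of −2.5 in both doses (SAP 1.4).

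*Three levels, arms sorted 200, 300, placebo.* Row 1 = 300 mg minus 200 mg = −2.5 − (−2.5) = 0. Row 2 = placebo minus 200 mg = 0 − (−2.5) = +2.5. These lie 2.5 and 5.0 points from the group LS mean differences that the SAP reports beside them. The sort depends on the labels chosen: arms labelled Placebo and SOM3355 (followed by the dose) sort with placebo first, and the code is then right.

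*Four levels, placebo first.* Row 1 = 200 mg at V3 minus placebo at V4. Row 2 = 300 mg at V2 minus placebo at V4. The documents give no time course, so a range is needed:

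- Flat placebo at 0 and full effect from Week 3: −2.5 − 0 = −2.5 in both rows, no error.
- Assumed placebo −0.5, −0.8, −1 at V2, V3, V4, with 20% and 60% of the effect at V2 and V3: row 1 = (−0.8 − 1.5) − (−1) = −1.3; row 2 = (−0.5 − 0.5) − (−1) = 0.0.

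**Sample size.** The plan's 39 per arm reproduces by noncentral t (SD 3.5, two-sided 0.025): 79.4% power at 38 and 80.5% at 39. It does not depend on this point.

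**The case for a change.** The best case for a change is that a SAP should fix its primary model in words and not leave it to be decoded from coefficients. Section 4.7.2.3 defines percentage change, not the primary response, and the listing order does not govern CLASS. Both rows sum to zero in every layout, so a sum check would not reveal a fault. A few lines of text would settle it.

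Part of this stands. Section 4.7.1 alone names neither the three levels nor the arm order, and stating them would be a harmless editorial improvement. It would not alter the model, the coefficients, the data or the result. The checks on output are also stronger than a row sum: the elsm option prints the coefficients, group LS means are reported with the differences, and SAP section 5 has the trial statistician check consistency and plausibility.

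The other two places are wording. Section 4.7.2.2 uses the V4 and V5 values for end of maintenance and also labels V5 alone as end of maintenance, so the reference to V5 in 3.6 can be read as shorthand. The reference in 4.12 still names the primary endpoint, and only 4.7.1 has that heading. Section 4.7.2.5 says only that its analysis is similar to the primary one, so whether TMS, gait and dystonia use the V4/V5 mean is a separate question that this point does not settle.

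**Conclusion.** The concern does not hold as a defect in the planned analysis. Under the layout that the SAP's own text, labels and coefficients imply, both contrasts are correct and the error is zero. The unstated visit levels and arm order are programming detail that a competent analyst fills in one way, and the reference in 4.12 is a clerical slip.

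This rests on reading 4.7.1 as a whole, together with 4.7.2.3. The wrong answers shown above need a miscoding that contradicts that reading and then goes unnoticed. Their size rests on an assumed label sort or on time courses that the documents do not give, and one such course gives no error at all. They do not measure a flaw in the plan.
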